### **8.2.2.- PREOP (PRE-OPERATIVE) and POST-OPERATIVE DAYS (DAY 1, DAY 2, DAY 3, DAY 4 AND DAY 6)**

These boxes include the variables collected PREOPERATIVELY and during the established postoperative days. These variables are:

- HR (HEART RATE): continuous variable expressed in beats per minute.
- RR (RESPIRATORY RATE): continuous variable expressed in breaths per minute.
- Ta (TEMPERATURE): continuous variable expressed in OC.
- VAS (VISUAL ANALOGUE SCALE): Scale used to assess the degree of pain. Ordinal variable from 1 to 10.
- TAS (SYSTOLIC ARTERIAL PRESSURE): continuous variable expressed in mmHg.
- DBP (DIASTOLIC ARTERIAL PRESSURE): continuous variable expressed in mmHg.
- SAT O2 (OXIGEN SATURATION): continuous variable expressed in %.
- DIURESIS (DIARIES VOLUME OF DIURESIS): continuous variable expressed in ml/day.
- LEUKES (LEUKOCYTES): continuous variable expressed in number/ $\mu$ L.
- LYMPHOS (LYMPHOCYTES): continuous variable expressed in number/ $\mu$ L.
- NEUTRAL (NEUTROPHILS): continuous variable expressed in number/ $\mu$ L
- HB (HEMOGLOBIN): continuous variable expressed in g/dL.
- PLATELET (PLATELET): continuous variable expressed in number/ $\mu$ L
- CREATININE (CREATININE): continuous variable expressed in mg/dL.
- PROTEINS (PROTEINS): continuous variable expressed in g/dL.
- ALBUMIN (ALBUMIN): continuous variable expressed in g/dL.
- CRP (C-REACTIVE PROTEIN): continuous variable expressed in mg/L.
- PROCAL (PROCALCITONIN): continuous variable expressed in ng/mL.
- IL 6 (INTERLEUKIN 6): continuous variable expressed in pg/ml.
- QUICK (QUICK INDEX): continuous variable expressed in %.

### **8.2.3.- RESULTS**

- ORAL TOLERANCE BEGINNING DAY: postoperative day number on which the patient begins to tolerate food and/or water orally. Continuous variable expressed in days.
- DISCHARGE DATE (DATE OF INTERVENTION): in day/month/year format

- CLAVIEN DINDO COMPLICATION (CLASSIFICATION OF POSTOPERATIVE COMPLICATIONS ACCORDING TO CLAVIEN-DINDO): Categorical variable divided into the following categories:

- NO COMPLICATION: If this complication did not occur.
- I: Any deviation from the normal postoperative course WITHOUT the need for pharmacological treatment or surgical, endoscopic and radiological interventions Acceptable therapeutic regimens are drugs such as antiemetics, antipyretics, analgesics, diuretics and electrolytes and physiotherapy. This grade also includes open wound infections at the patient's bedside.
- II: Requires pharmacological treatment with medications other than those authorized for grade I complications. Blood transfusions and total parenteral nutrition are also included.
- IIIa: Requires surgical, endoscopic or radiological intervention with local anesthesia.
- IIIb: Requires surgical, endoscopic or radiological intervention under general anesthesia.
- IVa: Life-threatening complication (including central nervous system complications: cerebral haemorrhage, cerebral infarction, subarachnoid haemorrhage, but excluding transient ischemic attacks) requiring Intermediate/Intensive Care Unit management. Single organ dysfunction (includes dialysis)
- IVb: Life-threatening complication (including central nervous system complications: cerebral haemorrhage, cerebral infarction, subarachnoid haemorrhage, but excluding transient ischemic attacks) requiring Intermediate/Intensive Care Unit management. Multi-organ dysfunction.
- V: Death of the patient.

- NECROSIS of the PLASTY: Categorical variable divided into the following categories according to the consensus definitions of the Consensus Group on Complications of Esophagectomy (ECCG) (27):

- NO: If this complication did not occur.
- I: Focal necrosis of the graft identified endoscopically, which does NOT require surgical treatment.
- II: Focal necrosis of the graft identified endoscopically, requiring surgical treatment, but not esophageal diversion
- III: Extensive necrosis of the graft, which requires surgical treatment with resection of the graft and esophageal diversion.

- DIA Dx NECROSIS (DAY OF DIAGNOSIS OF PLASTY NECROSIS): ordinal variable that shows the number of the postoperative day on which the diagnosis of plasty necrosis occurred

- EDA Dx NECROSIS (DIAGNOSIS OF PLASTY NECROSIS BY ENDOSCOPY): Dichotomous variable: YES/NO.

- CAT Dx LEAK (DIAGNOSIS OF PLASTY NECROSIS BY CAT): Dichotomous variable: YES/NO.

- CHYLOTHORAX: Categorical variable divided into the following categories according to the consensus definitions of the Consensus Group on Complications of Esophagectomy (ECCG) (27):

- NO: If this complication did not occur.
- Ia: Debit less than 1 liter per day - Treatment: changes in the enteral diet
- Ib: Debt greater than 1 liter per day - Treatment: changes in the enteral diet
- IIa: Debt less than 1 liter per day – Treatment: total parenteral nutrition
- IIb: Debt greater than 1 liter per day – Treatment: total parenteral nutrition
- IIIa: Debit less than 1 liter per day - Treatment: interventional radiology or surgery
- IIIb: Debt greater than 1 liter per day - Treatment: interventional radiology or surgery

- DAY Dx CHYLOTHORAX (DAY of DIAGNOSIS OF CHYLOTHORAX): ordinal variable that shows the number of postoperative day on which the diagnosis of chylothorax occurred.

- RECURRENT INJURY: Categorical variable divided into the following categories according to the consensus definitions of the Esophagectomy Complications Consensus Group (ECCG) (27):

- NO: If this complication did not occur.
- Ia: Transient unilateral lesion that does NOT require treatment (dietary modifications allowed)

- Ib: Transient bilateral lesion that does NOT require treatment (dietary modifications allowed)
- IIa: Unilateral injury that requires scheduled and deferred surgical treatment (such as thyroplasty or medialization procedure)
- IIb: Bilateral lesion that requires scheduled and deferred surgical treatment (such as thyroplasty or medialization procedure)
- IIIa: Unilateral lesion requiring urgent or preferential surgical treatment due to episodes of aspiration or respiratory problems (such as thyroplasty or medialization procedure)
- IIIb: Bilateral lesion requiring urgent or preferential surgical treatment due to episodes of aspiration or respiratory problems (such as thyroplasty or medialization procedure)
  
- DAY Dx RECURRENT INJURY (DAY of DIAGNOSIS OF THE RECURRENT NERVE INJURY): ordinal variable that shows the postoperative day number on which the diagnosis of the recurrent nerve injury occurred.
  
- AF (ATRIAL FIBRILLATION): Dichotomous variable: YES/NO.
  
- DAY Dx AF (DAY of DIAGNOSIS OF ATRIAL FIBRILLATION): ordinal variable that shows the postoperative day number on which the diagnosis of atrial fibrillation occurred.
  
- RESPIRATORY INFECTION: Dichotomous variable: YES/NO.
  
- DAY Dx INFEC RESP (DAY of DIAGNOSIS OF RESPIRATORY INFECTION): ordinal variable that shows the number of the postoperative day on which the diagnosis of respiratory infection occurred.
  
- SURGICAL SITE INFECTION (NOT WOUND): Dichotomous variable: YES/NO.
  
- DAY Dx SURGICAL SITE INFECTION (DAY OF DIAGNOSIS OF SURGICAL SITE INFECTION): ordinal variable that shows the number of postoperative day on which the diagnosis of surgical site infection occurred, not including wound infection.
  
- WOUND INFECTION: Dichotomous variable: YES/NO.
  
- DAY Dx WOUND INFECTION (DAY OF SURGICAL WOUND INFECTION DIAGNOSIS): ordinal variable that shows the postoperative day number on which the diagnosis of wound infection occurred.
  
- MORTALITY: Dichotomous variable: YES/NO.
  
- MORTALITY DAY: ordinal variable that shows the postoperative day number on which death occurred.
  
- CAUSE OF MORTALITY: categorical variable with the following categories:
  - Heart problems: including acute myocardial infarction, heart failure, malignant arrhythmias.
  - Respiratory problems: which includes pneumological conditions with respiratory failure that cannot be corrected
  - Neurological problems: including massive stroke, cerebral edema or brain death.
  - hemorrhagic shock
  - Sepsis and septic shock
  - Tumor progression: defined as progressive deterioration of the patient directly related to the oncological process.
  - Other: Free text to write a summary of the cause of the patient's death, if it cannot be included in the previous categories.
  
- READMISSION: Dichotomous variable: YES/NO.
  
- READMISSION DAY: ordinal variable that shows the postoperative day number on which the readmission occurred.

- CAUSE OF READMISSION (WRITE): Free text to write in summary the cause of the patient's readmission.

#### **8.2.4.- LEAK TREATMENT**

- RESOLUTION (RESOLUTION OF THE LEAK): Achievement of healing or closure of the fistula or dehiscence. Dichotomous variable: YES/NO.

- RESOLUTION DAY: ordinal variable that shows the postoperative day number on which the resolution or closure of the fistula occurred.

- ENDOSCOPY 1: application of some endoscopic treatment for the resolution of AF. Categorical variable divided into the following categories:

- NOT
- CLIPS / SUTURE
- ENDOPROSTHETICS
- ENDOSPONGE
- OTHERS

- ENDOSCOPY 2: application of a second endoscopic treatment for the resolution of AF. Categorical variable divided into the following categories:

- NOT
- CLIPS / SUTURE
- ENDOPROSTHETICS
- ENDOSPONGE
- OTHERS

- SURGERY 1: surgical intervention to try to resolve the AF. Categorical variable divided into the following categories:

- NOT
- WASHING + DRAINAGE
- JEJUNOSTOMY
- CLOSURE +/- COVERAGE FLAP
- EXTERIORIZATION (KERH OR SIMILAR)
- ESOPHAGEAL EXCLUSION
- OTHER

- SURGERY 2: surgical intervention added to the previous one to try to resolve the AF. Categorical variable divided into the following categories:

- NOT
- WASHING + DRAINAGE
- JEJUNOSTOMY
- CLOSURE +/- COVERAGE FLAP
- EXTERIORIZATION OF THE AF (KERH TUBE)
- ESOPHAGEAL EXCLUSION
- OTHER

- SURGERY 3: surgical intervention added to the previous ones to try to resolve the AF. Categorical variable divided into the following categories:

- NOT
- WASHING + DRAINAGE

- JEJUNOSTOMY
- CLOSURE +/- COVERAGE FLAP
- EXTERIORIZATION OF THE AF (KERH TUBE)
- ESOPHAGEAL EXCLUSION
- OTHER

- RX INTERVENTIONISM 1 (INTERVENTIONIST RADIOLOGY): Intervention by Interventional Radiology to try to resolve AF and its associated complications. Categorical variable divided into the following categories:

- NOT
- DRAINAGE
- JEJUNOSTOMY
- ENDOPROSTHESIS
- OTHERS

- RX INTERVENTIONISM 2 (INTERVENTIONIST RADIOLOGY): Interventional Radiology intervention added to the previous one to try to resolve AF and its associated complications. Categorical variable divided into the following categories:

- NOT
- DRAINAGE
- JEJUNOSTOMY
- ENDOPROSTHESIS
- OTHERS

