## OBJECTIVES

Based on the hypothesis of the study, the main and secondary objectives of this study are established:

- Main goal:

\*Design a predictive model based on clinical and analytical variables that allow identifying patients with a high risk of anastomotic leak (main variable) during the postoperative period of esophagogastric surgery.

- Secondary objectives:

\* Design a predictive model based on clinical and analytical variables that allow identifying patients at high risk of other major complications (Clavien-Dindo greater than 3) during the postoperative period of esophagogastric surgery.

\* Individually describe the postoperative evolution of the clinical and analytical parameters studied in patients without major complications or AF and those who did suffer from any of them.

\* Describe the complications and types of AF diagnosed in the study.

\* Assess the day AF was diagnosed and the treatment used for its possible resolution.

\* Assess the day AF was diagnosed and hospital stay.

\* Compare the preoperative Glasgow prognostic score (mGPS) and the biochemical value of inflammatory markers (CRP, Interleukin 6 (IL-6) and procalcitonin) and the appearance of AF.

\* Assess the AF resolution capacity of each technique used.

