## **8.2.- PARTS of the DATABASE**

After opening the REDCAP application of the AEC, you can access the data set and the different variables to be collected at each moment of the care process and which will be described in more detail below:

The main outcome variable of the study is ANASTOMOTIC LEAKAGE, a categorical variable divided into the following categories, according to the consensus definitions of the Consensus Group on Complications of Esophagectomy (ECCG) (27), which in this study will be applicable both to fistulas occurred after esophagectomy and after gastrectomy:

- NO: If this complication did not occur.
- I: Defect that does not require specific treatment or that can be treated medically or with diet modification
- II: Defect that requires some intervention, but not surgical, such as: drainage by interventional radiology, prosthesis placement, opening of the wound at the bedside, compression or wound healing.
- III: Defect requiring surgical intervention

In relation to this variable, the following data are also included in the study:

- DAY Dx LEAK (DAY of DIAGNOSIS OF THE ANASTOMOTIC LEAK: ordinal variable that shows the number of the postoperative day on which the diagnosis of the anastomotic leak occurred.
- EDA Dx LEAK (LEAK DIAGNOSIS THROUGH ENDOSCOPY): Dichotomous variable: YES/NO.
- CAT Dx LEAK (DIAGNOSIS OF LEAK BY CAT): Dichotomous variable: YES/NO.

The rest of the variables collected in this study are:

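### The leak-treatment fields do not allow closure to be attributed to a technique in patients treated with several modalities, and no attribution rule is planned

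*Combined protocol and SAP*

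**What the plan says.** The last secondary objective in the protocol's Objectives section is: "Assess the AF resolution capacity of each technique used" (AF is the protocol's abbreviation for anastomotic leak in this context). The data for it are in section 8.2.4, Leak treatment:

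- One outcome per patient: "RESOLUTION (RESOLUTION OF THE LEAK): Achievement of healing or closure of the fistula or dehiscence", recorded yes/no.
- One date per patient: "RESOLUTION DAY: ordinal variable that shows the postoperative day number on which the resolution or closure of the fistula occurred".
- Two endoscopy fields: "ENDOSCOPY 1: application of some endoscopic treatment for the resolution of AF" and "ENDOSCOPY 2: application of a second endoscopic treatment for the resolution of AF".
- Three surgery fields, beginning "SURGERY 1: surgical intervention to try to resolve the AF" and "SURGERY 2: surgical intervention added to the previous one to try to resolve the AF", with a third of the same form.
- Two interventional radiology fields, whose stated purpose covers the leak and also complications associated with it.

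Each procedure field holds a category of procedure and nothing else. Section 8.2 adds the day the leak was diagnosed and grades the leak by the treatment it needed; the top grade reads "III: Defect requiring surgical intervention". The Data analysis section plans descriptive summaries, and tests and models for the occurrence of leak and of major complications. It gives no denominator, estimator or attribution rule for resolution by technique.

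**The concern.** A closure rate per technique needs to know, for each procedure, whether the leak closed after it without another attempt at closure. The fields as written give this only in simple cases. When an endoscopic treatment, a drainage and an operation all appear for one patient, the same closure flag sits beside all three. Nothing says which came last or which was meant to close the leak.

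The obvious tabulation, the percentage resolved among patients who had each technique, would count a failed technique as a success whenever another one rescued it. The other simple option, keeping only patients with one technique, drops exactly those failures that went on to something else. Both can put misleading closure rates into a publication. An analyst working from the database afterwards could not undo this, because the missing information was never entered.

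**Working it through.** The plan states no figure for resolution by technique, so there is none to reproduce. The check is a count of fields followed by an illustration with assumed rates.

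**Field count (section 8.2.4).** Endoscopy 2 + surgery 3 + radiology 2 = 7 procedure fields. Procedure days: 0. Outcomes per procedure: 0. Resolution flags: 1. Resolution days: 1.

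**What order can be recovered.** Numbering suggests the sequence within a modality, although a surgical or radiological procedure described as added to the previous one could belong to the same session. Nothing orders the modalities against each other. If all seven fields were filled and the order within each modality were taken as known, 7!/(2! × 3! × 2!) = 5,040/24 = 210 sequences would fit the same record. The day of leak diagnosis dates no procedure.

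**Size of the distortion.** Assumptions, not taken from the documents: technique A is used first and closes a proportion a; a share f of its failures goes on to technique B, which closes a proportion b; B is used only as rescue.

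- Shared flag credited to A: a + (1 − a) × f × b.
- Patients treated with A only: a / [a + (1 − a) × (1 − f)].

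With a = 0.50 and b = 0.70 these become 0.50 + 0.35f and 0.50 / [0.50 + 0.50(1 − f)]:

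| Share of A's failures rescued (f) | True rate for A | Flag credited to A | A-only patients |
|---|---|---|---|
| 25% | 50% | 58.75%, about 59% | 0.50/0.875 = 57% |
| 50% | 50% | 67.5%, about 68% | 0.50/0.75 = 67% |
| 75% | 50% | 76.25%, about 76% | 0.50/0.625 = 80% |
| 100% | 50% | 85% | 0.50/0.50 = 100% |

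Both routes are biased upward for A at every f above zero.

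**Range over the assumed rates.** With f = 1 the overstatement from crediting the flag is (1 − a) × b. For a from 0.30 to 0.70 and b from 0.50 to 0.90 it runs from 0.30 × 0.50 = 15 points to 0.70 × 0.90 = 63 points. For smaller f it shrinks in proportion.

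**Ranking.** B, used only as rescue, reads its true 70%. A overtakes it when 0.50 + 0.35f > 0.70, that is f > 0.20/0.35 = 57%. With a = 0.50 and b = 0.80, credited A is 0.50 + 0.40f, and reversal needs f > 0.30/0.40 = 75%. So a reversed ranking is possible but depends on most failures being rescued.

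**What per-procedure data would give.** If success means closure with no later attempt at closure, A is credited with a only: 50% in every row of the table.

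**The case against.** The strongest reply is that the data are not useless and the plan does not commit itself to a wrong rate. Several parts of this stand.

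- A reader might infer that the objective cannot be answered at all. The documents do not support that. Where a patient had one technique, the flag belongs to it; within one modality the numbering gives some sequence; and resolution by treatment combination can be tabulated from the existing fields. What is lost is attribution when several modalities were used.
- A reader might infer that the plan will credit closure to every technique. No section says so. The distortions above follow only from analyses the plan leaves open.
- A reader might point to grade as the fault, since the top grade is defined by surgery. The plan does not propose to stratify resolution by grade, and the grading is an adopted consensus definition. Grade is relevant only because it offers no independent severity measure with which to compare techniques. Confounding by severity would remain even with perfect procedure dates.
- Defining success as closure with no further procedure of any kind would be unfair in the other direction. The fields include drainage and jejunostomy, and radiology also covers associated complications, so a supportive procedure would be scored as failure of the technique before it. The remedy has to separate the two purposes.

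What does not stand is the suggestion that this is only missing analysis detail. A rule written later cannot recover an order that was not recorded. The single-technique subset, the natural fallback, is itself selected and biased upward. The protocol also records a day for leak, necrosis, chylothorax, nerve injury, atrial fibrillation, infections, death and readmission; leak procedures, which have their own objective, are the exception.

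**Conclusion.** The point holds for patients treated with more than one modality: data collected exactly as section 8.2.4 describes cannot show the order of their procedures or which one preceded closure, and no attribution rule is planned. With assumed true rates of 50% and 70%, the first technique would read 59% to 85% if the flag were credited to it, or 57% to 100% in single-technique patients, as the share of failures rescued goes from 25% to 100%. These figures show direction and scale only; the documents give no closure rates and no rescue share.

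The number of patients affected is also unknown. A reader might take all leak patients as affected, but patients managed without any procedure and those with a single technique are not.

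This concerns one secondary, descriptive objective. The primary leak prediction model does not use these fields and is unaffected. It is a cheap improvement worth making, not a flaw in the main analysis.

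**What to change.** 1. Add two items to each of the seven procedure fields: the postoperative day it was performed, and whether it was aimed at closing the leak or was supportive (for example drainage of a collection or feeding access).
2. Define technique success as closure with no later closure-directed procedure. Report it descriptively by technique and by order of use.
3. Report patients with several procedures also by treatment combination. Where two closure-directed procedures fall on the same day, report them only as a combination.
4. State that techniques will not be ranked, because the choice of technique follows severity and grade is defined by treatment.

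If the database cannot be changed, restate the objective as resolution by treatment combination, which the existing fields support.

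Cost: up to 7 × 2 = 14 short REDCap fields, completed only for leak patients, and a paragraph of analysis text. Researchers at each center have access to the medical records (Schedule, item 5.5), so the items could also be completed for patients already entered. The downside beyond data entry is some judgement in labelling a procedure as closure-directed or supportive; a short written instruction to centers would limit variation. Nothing here changes patient care.

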## DATA COLLECTION AND ANALYSIS

### 1.- Data collection

Prior to being included in this study, the patient must have received and understood the information provided about the procedures to be performed. For this, an information sheet will be provided (Annex 1), and the patient must accept and sign the informed consent to voluntarily participate in the study (Annex 2). The selection and inclusion of patients will be carried out by the specialist doctors of each center according to the inclusion and exclusion criteria defined above.

In each center there will be a specialist physician who will be the coordinator or person in charge of updating and updating the database created for the development of this study.

Data collection will take place in four stages:

- 1.- First stage: collection of the patient identification data and the variables included in the GENERAL and PRE-OPERATIVE DATA section.
- 2.- Second time: collection of data that refer to the surgical intervention (within the GENERAL DATA section).
- 3.- Third time: collection of patient data during the postoperative period (within the sections of the different postoperative days and RESULTS)
- 4.- Fourth time: collection of patient data at 30 and 90 days during follow-up.

It is expected that, in most cases, the main objective can be quantified after the end of the hospital stay and the collection of data from the first, second and third times. The secondary objectives will be completed mostly once the hospital stay is over, completing them after follow-up and the fourth time of data collection.

